5.1 Enrollment

Before the study begins, the investigator must clearly and verbally explain the study's circumstances, potential risks, and benefits to the patient or their authorized representative. The patient or their authorized representative and the investigator must sign and date the informed consent form. The patient can only enter the screening process and subsequently participate in the study after signing the informed consent form.

After signing the written informed consent, the patient will be assessed to determine if they meet the study criteria:

1. Patient's medical history;
2. Vital signs;

5.2 Randomization and Blinding

According to the principle of complete randomization, 60 patients will be assigned to the experimental group and the control group.

5.3 Research Methods

The control group will receive conventional anti-infective and expectorant therapy, plus suction via suction catheter as needed (i.e., when dyspneic or when phlegm sounds are heard in the airway). The observation group will receive, in addition to the control group's treatment, bronchoscopic treatment 1-2 times, including sputum suction under endoscopy, lavage, and drug instillation. Specific procedure steps: Prepare for the bronchoscopy procedure. Under continuous nasal cannula oxygen and vital sign monitoring via ECG, administer Atropine Injection 0.5mg (National Drug Approval No. H37021468, Shandong Huixin Pharmaceutical Group Co., Ltd.) combined with Lidocaine Injection (National Drug Approval No. H20065387, China Otsuka Pharmaceutical Co., Ltd.) 0.1g via nebulization for local anesthesia. Insert the Olympus BF-P180 fiber bronchoscope routinely through the nostril, sequentially entering various levels of bronchi. Under direct vision, clear airway secretions, collect lavage fluid for bacterial culture and drug sensitivity testing. If sputum is thick and difficult to suction, lavage with normal saline

can be used. Simultaneously, select sensitive antibiotics for instillation therapy based on the bacterial culture results of the airway secretions. After completion, slowly withdraw the bronchoscope. Both groups will receive continuous treatment for 1 week. Throughout the process, closely monitor the patient's vital signs. If oxygen saturation falls below 80% or heart rate exceeds 130 beats/min, immediately withdraw the fiber bronchoscope and provide symptomatic treatment. Resume the subsequent procedure after vital signs stabilize.

5.4 Adverse Events

Record adverse events, the number of and reasons for trial dropouts in detail.

IV. Adverse Events

1. Classification of Adverse Events and Serious Adverse Events

Common adverse reactions during bronchoscopy include: laryngospasm, airway bleeding, pneumothorax, cardiac arrest, aspiration, hoarseness.

Medical Device Adverse Event: Any harmful event unrelated to the intended effect of a medical device that occurs during the normal use of an approved, qualified medical device, leading or potentially leading to human injury.

Among these, **death** and **serious injury events** must be reported to the monitoring agency. Serious injury refers to any of the following:

- ① Life-threatening;
- ② Resulting in permanent impairment of a body function or permanent damage to a body structure;
- ③ Necessitating medical or surgical intervention to prevent such permanent impairment or damage.

Subject Death: An event resulting in the death of a subject.

Life-Threatening: An event which, in the investigator's judgment, places the subject at immediate risk of death without medical intervention. It does not include an event that might have caused death had it occurred in a more severe form.

Hospitalization: An event resulting in admission to the hospital, regardless of length of stay. This does not include emergency room observation or outpatient clinic visits.

Prolongation of Hospitalization: An event that results in or prolongs a subject's hospitalization.

Persistent or Significant Disability/Incapacity: An event resulting in a condition that substantially disrupts the subject's ability to conduct normal life functions. This does not include relatively minor symptoms such as headache, nausea, vomiting, diarrhea, influenza, or accidental injury.

Important Medical Event: An event that may not be immediately life-threatening or result in death or hospitalization but, based on appropriate medical judgment, may jeopardize the subject and may require medical or surgical intervention to prevent one of the outcomes listed above (e.g., subject death, life-threatening, hospitalization, prolongation of hospitalization, congenital anomaly, or persistent disability/incapacity).

2. Severity

Physicians can use the following definitions to judge the severity of all adverse events and serious adverse events, serving as study endpoints/data cut-off points.

[Mild] The adverse event is transient, and the patient tolerates it easily.

[Moderate] The adverse event causes discomfort to the subject and interferes with the subject's normal activities.

[Severe] The adverse event significantly affects the subject's daily activities, may cause incapacitation, or is life-threatening.

3. Reporting of Serious Adverse Events

In the event of a Serious Adverse Event, regardless of whether it is related to the device or the control device, the physician must notify Olympus (China) Co., Ltd. within 24 hours of becoming aware of the event.

V. Ethics and Quality

Ethics committee approval will be obtained prior to the initiation of this study.

Before enrolling a patient, authorization must be obtained for the use and/or disclosure of personal and/or health data. To protect patient privacy, the patient's age will be recorded on the Case Report Form instead of the date of birth, and the patient's initials will be recorded on the Case Report Form.

The consistency of the collected Case Report Form data will be checked. Data queries will be issued for inconsistent data, requiring clarification by the physician.

VI. Data Management

Investigators must fill in the collected data into the Case Report Form according to the study protocol requirements. At the end of the study, the investigator will submit the Case Report Forms for all patients enrolled in this study to the data management center. These Case Report Forms must be complete and signed. The consistency of the collected Case Report Form data will be checked. Data queries will be issued for inconsistent data, requiring clarification by the physician.

VII. Statistical Analysis

1. Statistical Software

The data statistical work will be completed by a biostatistician using the statistical software SPSS 22.0.

2. Data Description

Measurement data will be expressed as mean \pm standard deviation ($\bar{x} \pm s$), using normality tests and t-tests. Enumeration data will be expressed as n (%), using the Chi-square test (χ^2 test). A P-value < 0.05 will be considered statistically significant.

3. Data Statistics

All hypothesis tests will be two-sided, and a P-value < 0.05 will be considered statistically significant. Baseline data will be evaluated for comparability between groups, using two-tailed statistical tests at the $\alpha=5\%$ level. Group comparisons for enumeration data will use the Chi-square test, and group comparisons for measurement data will use the t-test.

4. Statistical Analysis Plan

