Currently, there are no reports domestically or internationally on bedside bronchoscopy for the treatment of post-stroke dysphagia and SAP. This study aims to explore the application value and clinical safety of portable fiber bronchoscopy in non-severe SAP patients with dysphagia, and to evaluate whether bronchoscopic treatment can alleviate dysphagia symptoms, improve hypoxia, pulmonary infection, and SAP prognosis.

II. Study Objectives

Primary Objective: To observe the efficacy of bronchoscopic sputum suction + lavage therapy on post-stroke dysphagia and stroke-associated pneumonia.

Secondary Objectives: To compare National Institutes of Health Stroke Scale(NIHSS scores)(It is a standardized tool used to assess the degree of neurological deficits in patients with acute stroke, consisting of 15 items covering consciousness level, visual field, facial paralysis, limb movement, ataxia, sensory, language, and articulation disorders. The scoring range for each project is 0 to 4 points, with 0 indicating no defects and higher scores indicating more severe neurological deficits; The total score ranges from 0 to 42 points, with 0 indicating no neurological deficits and 42 indicating extremely severe deficits), Acute Physiology and Chronic Health Evaluation (APACHE) II scores(It includes three parts: acute physiology score (APS), chronic physiology score (CPS), and patient age score, with a total score of 0-

71 points. The higher the score, the more severe the patient's condition, the worse the prognosis, and the higher the mortality rate), CPIS scores (Clinical Pulmonary Infection Scores), Water Swallow Test scores(Grade I: able to drink without coughing within 5 seconds; Grade II: No coughing after drinking twice or more; Grade III: Can be consumed in one go but accompanied by coughing; Grade IV: Drink twice or more with coughing; Grade V: Frequent coughing and inability to finish all drinks. Grade I indicates normal, Grade II indicates suspicious, and Grade III or above indicates abnormal), C-reactive protein (CRP), Length of hospital stay, arterial partial pressure of oxygen (PaO_2), Height(m), Weight(Kg),Body Mass Index (BMI, Report BMI in kg/m^2 by combining weight and height) ,and overall clinical treatment efficacy between the two groups.

III. Study Plan

1. Study Population Selection

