4.1 Study Implementation Period: September 2019 --- September 2021

4.2 Study Observation Period: Observation for 7 days starting from enrollment.

5. Study Execution

This is a single-center, prospective, randomized, controlled, clinical study.

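### Outcomes are compared without baseline adjustment and the swallow grade has no assigned test; ANCOVA and one named ordinal analysis would add power at almost no cost

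*Combined protocol and SAP*

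**What the plan says.** The whole analysis specification is in VII.2 and VII.3; VII.4 says only who will do the work.

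- **Outcome tests (VII.3):** "Group comparisons for enumeration data will use the Chi-square test, and group comparisons for measurement data will use the t-test". No covariate, change score, stratified analysis, rank test or ordinal model is named anywhere.
- **Baseline data (VII.3):** "Baseline data will be evaluated for comparability between groups, using two-tailed statistical tests" at the 5% level. No other use is stated.
- **Normality (VII.2):** measurement data are handled "using normality tests and t-tests", with no alternative if normality fails.
- **Allocation (III.5.2):** "According to the principle of complete randomization, 60 patients will be assigned to the experimental group and the control group". No stratification or ratio is described.
- **Swallowing (II, Secondary Objectives):** the measure is introduced as "Water Swallow Test scores(Grade I: able to drink without coughing within 5 seconds", continues through five ordered grades, and ends with a cut: "Grade I indicates normal, Grade II indicates suspicious, and Grade III or above indicates abnormal".
- **Timing:** III.4.2 gives "Observation for 7 days starting from enrollment" without naming assessment days. In III.5.1, after consent, "the patient will be assessed to determine if they meet the study criteria", and only medical history and vital signs are then listed.

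**The concern.** There are two separate losses.

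**Precision.** NIHSS, APACHE II, CPIS, PaO2 and CRP can all be measured at entry and again at the end of observation. An unadjusted t-test on the final value leaves in the noise all the variation that the entry value could explain. Significance tests of baseline comparability do not recover it: they correct nothing, and the plan attaches no action to their result. With simple randomisation of 60 patients, a chance difference in baseline severity also passes straight into the treatment estimate.

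**An open choice for swallowing.** Post-stroke dysphagia is part of the primary objective, and the Water Swallow Test is the swallowing measure listed among the outcomes. The text supports three readings: a score (t-test), five categories (2×5 chi-square), or normal/suspicious against abnormal (2×2 chi-square). Nothing selects one, so the choice could be made after results are seen. The two chi-square readings discard the order of the grades wholly or partly.

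**Working it through.** **Inputs.** From the documents: N = 60 (III.2), two-sided 5% level (VII.3), five ordered grades with a cut at Grade III (II). The documents give no power, effect size, SD or correlation, so there is no planned figure to reproduce. Assumed: 30 per arm; correlation r between baseline and outcome of 0.3, 0.5 or 0.7; effects of 0.4 and 0.6 SD.

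**1. Power with and without adjustment.** ANCOVA reduces the residual SD to √(1 − r²). The noncentrality is d / [√(1 − r²) × √(2/30)], with √(2/30) = 0.258, on 58 df (t-test) or 57 df (ANCOVA). For d = 0.6 unadjusted, 0.6/0.258 = 2.32. At r = 0.5, 2.32/0.866 = 2.68. The equivalent unadjusted trial size is 60/(1 − r²).

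| | t-test | ANCOVA r = 0.3 | r = 0.5 | r = 0.7 |
|---|---|---|---|---|
| Variance factor 1 − r² | 1 | 0.91 | 0.75 | 0.51 |
| Equivalent unadjusted N | 60 | 66 | 80 | 118 |
| Power, 0.6 SD | 63% | 67% | 75% | 89% |
| Power, 0.4 SD | 33% | 36% | 42% | 57% |
| Difference with 80% power | 0.74 SD | 0.70 SD | 0.64 SD | 0.53 SD |

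A simulation of 40,000 trials per setting at 0.6 SD gave 62.5–62.9% for the t-test and 66.0%, 74.3% and 88.5% for ANCOVA. Under the null, both held their level (4.9–5.1% and 4.9–5.0%).

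The plan does not say whether the t-test would be applied to final values or to changes. A change score has variance factor 2(1 − r) = 1.4, 1.0 and 0.6 at these correlations, so it is worse than ANCOVA in each case.

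**2. Chance imbalance.** The probability of a baseline gap of at least 0.5 SD on a given measure is 2[1 − Φ(0.5/0.258)] = 2[1 − Φ(1.94)] = 5.3%. With the gap fixed at 0.5 SD, the simulated false-positive rate of the unadjusted t-test is 7.8%, 12.4% and 19.4% at r = 0.3, 0.5 and 0.7. At 0.25 SD it is 3.9–4.8%, and at 0.3 SD 5.3–5.7%. Averaged over all randomisations it is 5%.

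**3. Swallow grade.** Simulation, 6,000 trials per scenario, 30 per arm, proportional-odds shift. The assumed control percentages for Grades I–V are A: 10/20/30/25/15, B: 5/10/25/30/30, C: 20/30/25/15/10.

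| Test | OR 3: A / B / C | OR 2: A / B / C |
|---|---|---|
| 2×5 chi-square | 41 / 41 / 40% | 17 / 18 / 17% |
| Chi-square at Grade III | 55 / 43 / 53% | 26 / 18 / 26% |
| t-test on grade numbers | 66 / 65 / 62% | 32 / 32 / 31% |
| Rank test | 65 / 65 / 64% | 32 / 33 / 32% |

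Simulation error is at most about √(0.25/6000) = 0.6 percentage points (one standard error). A separate run at odds ratio 2.5, with partly different control distributions, gave the same ordering: about 50% for the rank test and the t-test, 28–30% for the 2×5 chi-square, and 35–43% for the split at Grade III.

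**The case against.** The strongest reply is that nothing here is an error. The t-test is valid under randomisation, and the plan states no power that could be contradicted. The size of the gain rests on correlations that the documents do not give: at r = 0.3 it is only 3 to 4 percentage points, and the largest figures need r = 0.7 over a week of active treatment. Large baseline gaps are uncommon, and moderate ones leave the error rate near 5%. For swallowing, the measure is listed as a score beside NIHSS and APACHE II, which points to the t-test, and that reading loses almost nothing against a rank test. Finally, the two-item list in III.5.1 concerns eligibility, and the case report form may specify baseline fields that the text does not show.

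Most of this stands, and it sets the limits of the point. This is a matter of efficiency, not bias. The gain is uncertain in size but not in direction, apart from the one degree of freedom lost when r is near zero. The swallow-grade loss arises only under the chi-square readings; what remains is that the plan leaves those readings open. On recording, VII.3 itself refers to baseline data, so some baseline measurement is intended, but no schedule in the text says which measures or when. The gain costs nothing extra only for measures that are in fact recorded at entry.

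**Conclusion.** The concern holds. The planned tests are valid but inefficient, and the swallow-grade analysis is ambiguous. With 30 per arm, baseline adjustment is worth the equivalent of about 6, 20 or 58 extra patients at assumed correlations of 0.3, 0.5 or 0.7 (66, 80 or 118 less 60). It also removes the effect of a chance difference in the adjusted measure. For swallow grade at odds ratio 3, under the assumed control distributions, the chi-square readings have roughly 10 to 24 percentage points less power than a rank test, while the t-test reading has about the same. No gain is claimed from adjusting swallow grade for its own baseline, because a water-drinking test is an entry criterion and may narrow the baseline range. The change is recommended; the validity of the trial does not depend on it.

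**What to change.** Amend VII.3 before any group comparison is seen:

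1. Replace the baseline significance tests with a descriptive table by group.
2. List the measures recorded at baseline and state the day of the outcome assessment, for example the end of the 7-day observation period.
3. For each of NIHSS, APACHE II, CPIS, PaO2 and CRP that is recorded at baseline, analyse the end-of-observation value by ANCOVA with group and the same measure at baseline. Fix the scale for CRP in advance (log if skewed).
4. Analyse Water Swallow grade as an ordered outcome, either by proportional-odds regression with baseline grade as covariate or by a rank-sum test stratified by baseline grade. Name one of the two, and exclude the unordered chi-square.
5. For outcomes with no baseline value of their own, such as length of stay, name the test in advance, including what replaces the t-test if normality fails.

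The cost is a few lines of text and one degree of freedom per ANCOVA. SPSS 22.0, already named in VII.1, fits both ANCOVA and ordinal regression. No extra patients are needed. A measure not currently recorded at baseline must either be added to the assessment schedule or be left unadjusted.

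### Clinical safety is an exploratory aim without a named measure or interval estimate; the default chi-square test is unreliable for sparse adverse events, and a non-significant result must not be read as safety

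*Combined protocol and SAP*

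**What the plan says.** The last paragraph of the background gives the aim: "This study aims to explore the application value and clinical safety of portable fiber bronchoscopy in non-severe SAP patients with dysphagia". Section II then states the primary objective as "To observe the efficacy of bronchoscopic sputum suction + lavage therapy on post-stroke dysphagia and stroke-associated pneumonia". The secondary objectives list scores, laboratory values, length of stay, body measurements and overall treatment efficacy. None is an adverse-event measure.

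Section III.5.4 requires adverse events and dropouts, with reasons, to be recorded in detail. Section IV.1 gives a non-exhaustive list: "Common adverse reactions during bronchoscopy include: laryngospasm, airway bleeding, pneumothorax, cardiac arrest, aspiration, hoarseness". Section IV also defines serious events, grades severity as mild, moderate or severe, and sets a 24-hour notification for serious adverse events. Section III.5.3 adds a procedural rule: "If oxygen saturation falls below 80% or heart rate exceeds 130 beats/min, immediately withdraw the fiber bronchoscope and provide symptomatic treatment". The procedure is resumed once vital signs are stable.

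Section VII does not mention adverse events. Its general rules for counts are "Enumeration data will be expressed as n (%), using the Chi-square test" (VII.2) and "Group comparisons for enumeration data will use the Chi-square test" (VII.3), with "All hypothesis tests will be two-sided, and a P-value < 0.05 will be considered statistically significant". It names no exact test, confidence interval, safety population or unacceptable event rate.

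**The concern.** Adverse-event counts are enumeration data, so the only inferential rule that reaches them is a chi-square test at 0.05. For an invasive procedure in about half of 60 patients, most such counts will be small. Three problems follow.

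- The chi-square approximation is poor at small expected counts.
- The test has little chance of flagging harm rates that would matter clinically.
- A between-arm test is a weak way to describe reactions tied to the procedure, because controls have no planned bronchoscopy. For those, the rate in the treated arm and its precision are the useful quantities.

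There is also a gap in counting. A scope withdrawal for desaturation or tachycardia is not on the reaction list, and a procedure that is resumed need not be a dropout. Such an episode may well be recorded as an adverse event, but nothing ensures that this happens consistently.

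At stake is the safety statement in the final report. If P is the only planned yardstick, a P of 0.05 or more could be taken as reassurance that the data do not give.

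**Working it through.** **Inputs from the documents.** Total N = 60 (Section III.2); two-sided alpha 0.05 and a chi-square test for counts (Section VII). The plan gives no event rate, margin or power, so it has no safety figure to reproduce.

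**Assumptions.** 30 per arm, varied below, because Section III.5.2 says only that randomization is complete. For the detection probabilities, a true control rate of 0%, the simplest case for a procedure-specific reaction.

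**1. Three events against none, 30/30.** With k events in n1 treated patients and 0 in n2 controls, Pearson chi-square = N·k·n2 / [n1·(N − k)].
- k = 3: 60·3·30 / (30·57) = 3.158, P = 0.076.
- Expected events per arm: 3·30/60 = 1.5.
- Fisher, two-sided: 2·C(30,3)/C(60,3) = 2·4060/34220 = 0.237, about three times the Pearson value.

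**2. Smallest count against 0 that reaches P < 0.05, 30/30.**
- Pearson: 4 v 0 (chi-square 4.286, P = 0.038).
- Fisher: 6 v 0 (P = 0.024); 5 v 0 gives 0.052.

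**3. Sensitivity of 3 v 0 to the split.**

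| Treated / control | Pearson P | Fisher P |
|---|---|---|
| 30 / 30 | 0.076 | 0.237 |
| 28 / 32 | 0.058 | 0.096 |
| 27 / 33 | 0.0495 | 0.086 |
| 25 / 35 | 0.036 | 0.067 |

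For 27/33: 60·3·33 / (27·57) = 3.860. Moving one patient between 28/32 and 27/33 changes the Pearson verdict. Fisher stays above 0.05 in all four rows.

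**4. Probability of flagging a true harm, 30/30, control rate 0%.** With X ~ Binomial(30, p):
- p = 10%: Pearson P(X ≥ 4) = 0.353; Fisher P(X ≥ 6) = 0.073.
- p = 5%: Pearson 0.061; Fisher 0.003.

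Averaged over the splits that simple 1:1 randomization of 60 patients can produce, the Pearson figures are 33% and 7%, so the low detection does not depend on an exact 30/30 split.

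**5. What an interval would show.** Exact (Clopper-Pearson) 95% limits:
- 0/30: upper limit 1 − 0.025^(1/30) = 11.6%.
- 3/30: 2.1% to 26.5%.
- Risk difference for 3/30 v 0/30: 10 points, Newcombe 95% CI −3.1 to 25.6.

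**The case against.** The best defence is that the plan already holds much of what a small exploratory study needs: event rates by arm as n (%), detailed recording, severity grades, and separate notification of serious events whatever any test shows. All of that stands. A reader might infer that there is no safety analysis beyond a chi-square test; the n (%) summary contradicts this. Grading and notification are not analyses, though, and none of these elements puts a bound on harm.

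A reader might also infer that the plan will treat a non-significant difference as proof of safety. No section says so. The chi-square rule reaches adverse events only by default, and the risk of misreading is a reason to specify the interpretation in advance.

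A third tempting reading is that the listed reactions can occur only with bronchoscopy. That fails for aspiration: the background names dysphagia as a major predisposing condition for it, and every enrolled patient has dysphagia. Controls also receive catheter suction. No control rates are given, which is why 0% is only an assumption above.

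Finally, the 30/30 split is assumed, and the Pearson result for 3 v 0 does reverse at 27/33. That is correct. It shows how fragile the test is here, and the detection probabilities barely change when averaged over splits.

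**Conclusion.** The point holds as a recommendation on analysis and reporting. Safety is a stated exploratory aim with no named measure, no safety population and no interval estimate, and the default test is unsuited to sparse events. At 30 per arm, 3 v 0 gives P = 0.076 or 0.237 depending on the test, and a true 10% v 0% is flagged about 35% (Pearson) or 7% (Fisher) of the time. These figures rest on the assumed split and a zero control rate.

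It would go too far to say that the trial cannot support any safety conclusion. The aim is only to explore, and graded counts with intervals can support a descriptive statement. What the trial cannot do is rule out clinically important harm or use P ≥ 0.05 as evidence of safety. That limit comes mainly from the sample size, so replacing chi-square with Fisher's test would correct the P value but not remove the limit.

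**What to change.** - In Section II, name safety as an exploratory secondary objective.
- In Section VII, for the bronchoscopy arm, report the number of patients with any reaction, with each reaction listed in Section IV.1, and with any scope withdrawal under the existing criteria of Section III.5.3 (thresholds unchanged). Give these by severity, each with an exact 95% confidence interval on the actual denominator.
- For events possible in both arms, such as aspiration, report the risk difference with its 95% confidence interval in place of relying on the chi-square P value.
- State that P ≥ 0.05 is not evidence of safety, and quote the upper confidence limit with each rate. For example, 0/30 would not exclude rates up to 11.6%.

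The cost is some wording, one CRF item for scope withdrawal and one table. No extra patients are needed, and the intervals for recorded reactions come from counts already planned. The downside is that the safety claim becomes weaker than a statement of no significant difference.
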